5.4.3.3 Abortions

Any abortion should be classified as a serious adverse event (as the Sponsor considers abortions to be medically significant), recorded on the Adverse Event eCRF, and reported to the Sponsor immediately (i.e., no more than 24 hours after learning of the event; see Section [5.4.2](#)).

5.4.3.4 Congenital Anomalies/Birth Defects

Any congenital anomaly/birth defect in a child born to a female patient exposed to study drug should be classified as a serious adverse event, recorded on the Adverse Event eCRF, and reported to the Sponsor immediately (i.e., no more than 24 hours after learning of the event; see Section [5.4.2](#)).

5.5 FOLLOW-UP OF PATIENTS AFTER ADVERSE EVENTS

5.5.1 Investigator Follow-Up

The investigator should follow each adverse event until the event has resolved to baseline grade or better, the event is assessed as stable by the investigator, the patient is lost to follow-up, or the patient withdraws consent. Every effort should be made to follow all serious adverse events considered to be related to study drug or study-related procedures until a final outcome can be reported.

During the study period, resolution of adverse events (with dates) should be documented on the Adverse Event eCRF and in the patient's medical record to facilitate source data verification.

All pregnancies reported during the study should be followed until pregnancy outcome. At the time of pregnancy outcome, reporting instructions provided in Section [5.4.3.1](#) should be followed.

5.5.2 Sponsor Follow-Up

For serious adverse events, adverse events of special interest, and pregnancies, the Sponsor or a designee may follow up by telephone, fax, electronic mail, and/or a monitoring visit to obtain additional case details and outcome information (e.g., from hospital discharge summaries, consultant reports, autopsy reports) in order to perform an independent medical assessment of the reported case.

5.6 POST-STUDY ADVERSE EVENTS

The Sponsor should be notified if the investigator becomes aware of any serious adverse event that occurs after the end of the adverse event reporting period (defined as LPLV), if the event is believed to be related to prior study drug treatment.

The investigator should report these events directly to the Sponsor or its designee, either by faxing or by scanning and e-mailing the Serious Adverse Event/Adverse Event of Special Interest Reporting Form with use of the fax number or e-mail address provided to investigators.

5.7 EXPEDITED REPORTING TO HEALTH AUTHORITIES, INVESTIGATORS, INSTITUTIONAL REVIEW BOARDS, AND ETHICS COMMITTEES

The Sponsor will promptly evaluate all serious adverse events and adverse events of special interest (see Section 5.2.3) against cumulative product experience to identify and expeditiously communicate possible new safety findings to investigators, IRBs, ECs, and applicable health authorities based on applicable legislation.

To determine reporting requirements for single adverse event cases, the Sponsor will assess the expectedness of these events using the following reference document:

- RO5543262 (Emicizumab) Investigator's Brochure

The Sponsor will compare the severity of each event and the cumulative event frequency reported for the study with the severity and frequency reported in the applicable reference document.

Reporting requirements will also be based on the investigator's assessment of causality and seriousness, with allowance for upgrading by the Sponsor as needed.

6. STATISTICAL CONSIDERATIONS AND ANALYSIS PLAN

6.1 DETERMINATION OF SAMPLE SIZE

The sample size for this study is based on clinical rather than statistical considerations, taking into account the limited number of patients with hemophilia A without inhibitors available for participation in clinical studies and in an effort to collect sufficient data to assess the safety and efficacy of emicizumab.

The sample size calculation is based on the evaluation of the primary efficacy endpoint, defined as the number of bleeds over time (i.e., bleed rate) with emicizumab (treatment group, λ_t) versus no prophylaxis (control group, λ_c), which are said to follow a negative binomial (NB) distribution. With consideration of enrollment feasibility, a sample size of 75 patients, assuming an allocation ratio of 2:2:1 (30 patients in each randomized treatment group and 15 patients in control group), will achieve a power of more than 90% assuming a mean ABR of 4 and 14 bleeds (with variances = mean \times 10) for the emicizumab treatment and control arms respectively, representing an expected 71% reduction in the ABR compared to the control arm. Initial sample size calculations were performed with East[®], Version 6 (Cytel, Cambridge, MA), assuming the patients from each treatment group are followed up to 0.5 units of time (i.e., 24 weeks).

However, the above approach to sample size calculation assumes similar follow-up for each patient. Because this is unlikely to be seen in the study, power was also estimated by simulation to account for different follow-up times among patients. Conducting simulations on the basis of an NB regression model including an offset variable to account for variable follow-up times, with all other assumptions remaining the same as

previously described, the sample size is projected to have greater than 90% power at the 2-sided 0.05 level of significance.

The analysis will include all enrolled patients regardless of their length of follow-up. Therefore, to ensure the analysis is based on sufficient follow-up data and with 2:2:1 treatment to control randomization, approximately 34 patients in each randomized emicizumab treatment arm (68 in total) and 17 patients in the control arm (approximately 85 patients in total) will be enrolled.

6.2 GENERAL

This section provides a general overview of the methods. If any of the items require a unique approach that differs from the general overview, then it will be noted in the appropriate section.

All continuous variables will be summarized using the following descriptive statistics: n (non-missing sample size), mean, standard deviation, median, maximum, and minimum. The frequency and percentages (based on the non-missing sample size) of observed levels will be reported for all categorical measures.

All summary tables will be structured with a column for each treatment arm and will be annotated with the total population size relevant to that table/treatment, including any missing observations.

Analyses will follow the principle of intention-to-treat (i.e., based on randomized population).

6.3 SUMMARIES OF CONDUCT OF STUDY

Flow of patients through the study will be displayed in a “CONSORT” diagram. A clear account of all patients who entered the study, who were enrolled and randomized, and who entered and completed each phase of the study will be displayed. In addition, reasons for premature discontinuations from study treatment and reasons for withdrawing from the study (e.g., during follow-up) will be described.

Variables from the eCRF used to establish how many patients reached the various stages of the study, how many dropped out and for what reasons will be described in the Statistical Analysis Plan (SAP).

6.4 SUMMARIES OF TREATMENT GROUP COMPARABILITY

Comparisons between the treatment arms of demographic data and baseline characteristics will be conducted to establish if any observed differences between the treatment arms are not due to imbalances in patient characteristics at baseline. Only descriptive analyses are planned, and no formal statistical tests will be applied.

6.5 EFFICACY ANALYSES

The primary and secondary efficacy analyses to evaluate the clinical effect of prophylactic emicizumab compared with no prophylaxis will include all randomized patients, with patients grouped according to the treatment assigned at randomization. For patients previously treated with prophylactic FVIII, the efficacy analysis will include all enrolled patients.

6.5.1 Primary Efficacy Endpoint

The primary efficacy objective is to evaluate the clinical effect of prophylactic emicizumab compared with no prophylaxis on the number of bleeds over time. The definition of a bleed is described in Section 4.5.8. The primary endpoint is based on treated bleeds.

The primary efficacy analysis will be conducted after all randomized patients (and a minimum of 40 patients previously treated with prophylactic FVIII) have completed

24 weeks in the study or the last randomized patient yet to complete 24 weeks in the study discontinues study participation, whichever occurs first, and using an intent-to-treat principle. The comparison of the number of bleeds over time between the randomized treatment arms will be performed using an NB regression model, which accounts for different follow-up times, with the patient's number of bleeds as a function of randomization and the time that each patient stays in the study included as an offset in the model. The model also includes the number of bleeds (< 9 or ≥ 9) in the last 24 weeks prior to study entry as a stratification factor in the randomization. This analytic model estimates the rate ratio, λ_t/λ_c , which quantifies the risk of bleeding associated with prophylactic emicizumab (λ_t) in comparison to no prophylaxis (λ_c). Statistical significance is controlled at the 2-sided, 0.05 alpha (α) level. Of note, hierarchical testing is used to account for multiple testing and the first test to be included in the hierarchy is the emicizumab 1.5 mg/kg/wk maintenance dose versus control. The second test will be 3 mg/kg/2wks maintenance dose versus control. The description below covers both hypotheses to be tested:

H_0 (null hypothesis): Rate Ratio = 1 versus H_1 (alternative hypothesis): Rate Ratio $\neq 1$.

The treatment effect therein is based on a contrast statement in the model with use of the SAS GENMOD procedure. Statistical significance at the prespecified alpha level will be based on a Wald testing procedure. Bleed rates for prophylactic emicizumab and no prophylaxis and the rate ratio will be presented and include 95% confidence intervals.

The number of bleeds can also be annualized for each patient using the following formula: $ABR = (\text{Number of bleeds during the efficacy period} / \text{Total number of days during the efficacy period}) \times 365.25$. If the NB model converges, Van Elteren test to compare the mean ABR between the randomized arms will be provided only as a sensitivity analysis. However, if the convergence of the NB model is not achieved or is questionable, the primary efficacy analysis will be based on the Van Elteren test of ABR.

A detailed description of the statistical methods that will be used for the primary and secondary efficacy analyses will be provided in the SAP.

6.5.2 Secondary Efficacy Endpoints

For all patients, the number of bleeds over time will be compared with the patient's historical bleed rate, recorded in the medical record, and/or for the duration of their participation in the non-interventional study using an NB regression model similar to the one described for the primary efficacy endpoint.

In addition, the number of all bleeds (treated and not treated), spontaneous, joint and target joint bleeds over 24 weeks' time between the emicizumab prophylaxis and no prophylaxis arms will be evaluated by an NB regression model, as specified for the primary efficacy endpoint.

The efficacy of prophylactic emicizumab treatment in the cohort of non-inhibitor patients previously treated with prophylactic FVIII will be evaluated to demonstrate that these patients remain adequately controlled on emicizumab. The mean ABR will be estimated for each patient using the NB model and the one-sided 97.5% CI constructed around the estimated overall mean ABR. If the upper limit of the CI is less than or equal to 6, the treatment regimen will be considered to provide adequate control. This endpoint will be included as the third test in the hierarchical testing strategy.

Adherence with the HRQoL and health status measures will be summarized at the end of the study.

HRQoL (using the Haem-A-QoL or the Haemo-QoL-SF) and health status (using the EQ-5D-5L) will be assessed on a regular basis, as per the schedule of assessments (scheduled).

Because different HRQoL measures (Haem-A-QoL and the Haemo-QoL-SF) are being used for the adult and adolescent patients, all calculations and analyses will be conducted separately for adults and adolescents. Scale scores for the Haem-A-QoL and Haemo-QoL-SF will be calculated and summarized descriptively for all time points in the study. The HRQoL scale scores for all patients will be evaluated after 24 weeks in the study, a timepoint that is consistent with other recent registrational studies in hemophilia (Lentz et al. 2013; Powell et al. 2013; Mahlangu et al. 2014) and analyses of such data (Santagostino et al. 2014; Wyrwich et al. 2015). For each treatment arm, ANCOVA model will be used to compare the 24-week and final assessments with the baseline scale scores for each HRQoL measure. Within-subject and between-group changes from baseline on the different HRQoL scale scores will also be calculated at 24 weeks and the final HRQoL assessment. Statistical analysis of the Haemo-QoL-SF endpoints will be subject to sufficient adolescent patients being enrolled in the study to make meaningful statistical comparisons. Further details will be provided in the SAP after the completion of enrollment into the study if deemed necessary.

For the assessments of the EQ-5D-5L, the number and percentage of patients in each of the five categories for each question for each group will be assessed. Changes in the EQ-5D-5L index utility score from baseline will also be compared between groups. In addition, summary statistics including mean, standard deviation, median, minimum and maximum will be displayed for the patients' health state using the EQ-VAS both within and between groups. The proportion of patients who report changes in each group exceeding the clinically meaningful threshold on the EQ-5D-5L index and EQ-VAS scores in each group will be reported at 24 weeks and the final, scheduled EQ-5D-5L assessment.

Secondary endpoints used for labeling and those that are solely for scientific interest will be specified in the SAP.

6.6 SAFETY ANALYSES

The safety analyses population will be based on all enrolled patients grouped according to the actual treatment received. For Arm C patients, all safety data reported up to the day prior to switching will be included in the 'control arm' safety summaries, and all safety data reported on or after the date of switching to active treatment will be reported separately.

Safety will be assessed through descriptive summaries of adverse events, laboratory test results (serum chemistry and hematology, including complete blood count with differential), ECGs, vital signs, and antibodies to emicizumab and FVIII.

To evaluate the overall safety of prophylactic emicizumab compared to no prophylaxis, the incidence of adverse events will be summarized and presented by System Organ Class mapped term, appropriate thesaurus level, and toxicity grade for each treatment arm.

For clinical laboratory data, summary statistics will be presented by treatment arm. In addition, shift tables describing changes from baseline will be presented using the WHO toxicity grading scale.

Data on the impact of immunogenicity (anti-emicizumab antibodies) on safety, efficacy, and/or clinical pharmacology and PK will be summarized adopting standard language/terminology (Shankar et al. 2014).

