During the study, individual bleeds will be captured as they occur, while HRQoL, health status, patient safety, patient preference and satisfaction, activity level, and days of school or work missed will be assessed as outlined in the schedule of assessments. Patients (or their caregiver) will be asked to record on an electronic, handheld device their bleeds (i.e., start date and time, reason, type, location, and associated symptoms of each bleed) and hemophilia-related medication use (i.e., start date and time, reason, type, dose of injection, and number of doses) at least weekly, when a bleed occurs, or when a hemophilia medication was taken at home or in the clinic.

Throughout the study, biomarkers related to thromboembolism (e.g., D-dimer, prothrombin 1.2 fragment) and emicizumab trough concentrations will be collected as per the schedule of assessments. Immunologic biomarkers (i.e., anti-emicizumab antibodies and anti-FVIII antibodies) will also be measured as per the schedule of assessments (see [Appendix 1](#)).

Exploratory PD biomarkers (e.g., aPTT, FVIII activity, thrombin generation assay) will be collected as per the schedule of assessments. As values for some of these tests are normalized by low plasma concentrations of emicizumab, a variety of assay formats (one stage, chromogenic) and modifications (predilution of patient plasma) will be investigated for assessment of PD response at higher emicizumab plasma concentrations. However, it is not expected that these biomarkers will be used to guide dosing or the selection of patients to be treated with emicizumab. Rather, these biomarkers may be used to identify a future assay for the monitoring of emicizumab activity.

Physical examinations, including Hemophilia Joint Health Score (HJHS; see [Appendix 8](#)), vital signs assessments, ECGs, and laboratory assessments will be collected as per the schedule of assessments and will be the same for all patients, with the exception that emicizumab PK and ADAs will not be measured in patients in Arm C prior to the switch to emicizumab treatment. Adverse events will be captured as they occur for the duration of the study.

All patients who receive emicizumab in the study will undergo PK assessments. A washout period from FVIII therapy is not required prior to inclusion because FVIII replacement does not interfere with emicizumab PK assessments, and some patients with hemophilia A require frequent dosing with FVIII to treat bleeds or for prophylaxis.

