4.3.2 Dosage, Dose Adjustment, and Administration

As discussed in Section 3.3.1, when each patient starts on prophylactic emicizumab, he or she will receive 3 mg/kg/wk for 4 weeks as loading doses, followed by 1.5 mg/kg/wk or 3 mg/kg/2wks, for a total of at least 24 weeks and as long as they continue to derive sufficient clinical benefit.

Patients in Arms A or B with ≥ 2 qualifying bleeds within 24 weeks, may have the opportunity to increase their emicizumab maintenance dose to 3 mg/kg/wk starting on Week 25, if they receive approval from the Medical Monitor. Qualifying bleeds are defined as spontaneous, verified by investigator (e.g., by imaging or physical examination) and occurring while on prophylactic emicizumab at steady-state on the maintenance dose (after the Week 5 visit). Similarly, patients in Arm C who switch to emicizumab at Week 25 and experience ≥ 2 qualifying bleeds may have the opportunity to increase their emicizumab maintenance dose to 3 mg/kg/wk starting on Week 49, if they receive approval from the Medical Monitor.

Patients in Arm D who experience suboptimal control (two qualifying bleeds or more) on prophylactic emicizumab at the maintenance dose may have the opportunity to escalate to 3 mg/kg/wk immediately after the second qualifying bleed, with approval from the Medical Monitor.

If the investigator believes that a specific patient warrants dose escalation based on a different reason, they may discuss the case with the Medical Monitor for consideration and potential approval.

During study prolongation, each patient may choose a preferred emicizumab dosing regimen among those permitted (i.e., emicizumab 1.5 mg/kg/wk, 3 mg/kg/2wks, or 6 mg/kg/4wks) and continue on that dosing regimen until discontinuation from the study. A change from 1.5 mg/kg/wk to 3 mg/kg/2wks or 6 mg/kg/4wks can be initiated at the next scheduled treatment of the QW dosing regimen. A change from 3 mg/kg/2wks to 1.5 mg/kg/wk or 6 mg/kg/4wks can be initiated at the next scheduled treatment of the Q2W dosing regimen. A patient may switch dosing regimens only once. However, if the investigator believes that a patient warrants an additional change in dosing regimen, he or she may discuss the case with the Medical Monitor for consideration and potential approval.

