Appendix 1 Schedule of Assessments (cont.)

Schedule of Assessments—Arm C (Continued, at Time of Switch to Emicizumab)																		
	Wk 25	Wk 26	Wk 27	Wk 28	Wk 29	Wk 31	Wk 33	Wk 37	Wk 41	Wk 45	Wk 49	Every 8 Wks from Wk 57	Wk 73	Every 12 Wks from Wk 85	Every 24 Wks from Wk 97	Daily/ weekly ^a	Study Compl- etion/ ET	Safety F/U Visit ^b
Adverse events ^o	x	x	x	x	x	x	x	x	x	x	x	x	x	x	x		x	x
IMP management ^p	x	x	x	x	x	x	x	x	x	x	x	x	x	x	x		x	
HRQoL and health status ^q	x							x			x		x		x ^q		x	
PK assessment ^r	x	x	x	x	x	x	x	x	x	x	x	x	x	x	x		x	x
PD biomarkers ^s	x	x	x	x	x	x	x	x	x	x	x	x	x	x	x		x	x
Bone biomarkers (fasted) ^t	x							x			x		x		x		x	
Activity measure (optional) ^u	x										x							

BMQ=bleed and medication questionnaire; eCRF=electronic Case Report Form; EQ-5D-5L=EuroQoL Five-Dimension-Five Levels Questionnaire; ET=early termination; F/U=follow-up; FVIII=factor VIII; HRQoL=health-related quality of life; HJHS=Hemophilia Joint Health Score; IMP=investigational medicinal product, PD=pharmacodynamic; PK=pharmacokinetic; RCR=Roche Clinical Repository; SQ-ISHI=Satisfaction Questionnaire–Intravenous Subcutaneous Hemophilia Injection; wk=Week.

Notes: The maximum allowable time between screening and enrollment is 6 weeks; if the elapsed time between screening and enrollment is more than 6 weeks, screening must be repeated. All assessments should be performed within ± 2 days of the scheduled visit for the first 12 weeks and for Weeks 25–37 for Arm C patients who switch over, then ± 7 days thereafter. Clinic visits should coincide with the day of emicizumab dosing, and on those days the dose should be administered after blood draws and other assessments are conducted. Unscheduled assessments may be performed at the discretion of the investigator and as clinically indicated. Except for the bleed/injection questionnaire, HRQoL, and health status, all other patient data will be collected during office or nurse visits. Evaluation at Weeks 25 or 49 will occur after a full 24 or 48 weeks in the study. Study completion evaluation occurs when a patient discontinues emicizumab or transitions into another study.

^a Patients will complete the Bleed/Medication Questionnaire at least weekly and at the time of a bleed, or when they take a hemophilia-related medication (including emicizumab). Arm B patients should indicate at least weekly whether or not they had a bleed.

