Appendix 1 Schedule of Assessments (cont.)

-
- ⁱ Concomitant medications (e.g., extra pain medication with bleed) will be asked about at the time of the monthly assessment, excluding treatments for bleeds (i.e., FVIII and other medications to treat bleeds), which will be collected on the bleeding questionnaire. Hemostatic medications to treat or prevent bleeds in the week prior to starting emicizumab will also be collected and during Week 1 for patients in Arm D who continue their prior FVIII prophylaxis for the first week of the study.
- ^j Performed locally. If screening ECG is abnormal, repeat at Week 1 (or Week 2 [or Week 5 for Arm C] if Screening and Week 1 occur on the same day), otherwise do not repeat. ECGs will also be performed 4–8 and 24 weeks after starting emicizumab or dose escalation (up-titration), as well as at study completion/early termination.
- ^k Patient must have a documented local inhibitor test with negative result (<0.6 BU) at screening or within the 8 weeks prior to enrollment. Starting at Week 1, all subsequent anti-FVIII antibodies will be measured at a central laboratory using an aliquot of the citrate plasma collected for PD biomarker assessments, so a separate blood draw is not necessary. Please consult the central laboratory services manual for details.
- ^l Samples to detect anti-emicizumab antibodies will be collected prior to emicizumab administration at every clinic visit. However, only samples from the following visits will be analyzed initially: (Arms A, B, and D) immediately prior to the first injection at Week 1, every 8 weeks from Weeks 9–49, every 12 weeks starting from Week 61, and at the 24-week post-emicizumab safety follow-up visit following initiation of emicizumab; Arm C immediately prior to the first injection at Week 25, every 8 weeks from Weeks 33–73, every 12 weeks starting from Week 85, and at the 24-week post-emicizumab safety follow-up visit following initiation of emicizumab. If any of these samples are positive and/or if there is suboptimal clinical response or low pharmacokinetic exposure, the remaining collected samples may be analyzed for anti-emicizumab antibodies. Anti-emicizumab antibodies may also be drawn at the time of systemic hypersensitivity events.

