#### **Safety Analysis**

The safety analyses population will be based on all enrolled patients grouped according to the actual treatment received. For Arm C patients, all safety data reported up to the day prior to switching will be included in the 'control arm' safety summaries, and all safety data reported on or after the date of switching to active treatment will be reported separately.

Safety will be assessed through descriptive summaries of adverse events, laboratory test results (serum chemistry and hematology, including complete blood count with differential), ECGs, vital signs, and antibodies to emicizumab and FVIII.

To evaluate the overall safety of prophylactic emicizumab compared to no prophylaxis, the incidence of adverse events will be summarized and presented by System Organ Class mapped term, appropriate thesaurus level, and toxicity grade for each treatment arm.

For clinical laboratory data, summary statistics will be presented by treatment arm. In addition, shift tables describing changes from baseline will be presented using the WHO toxicity grading scale.

Data on the impact of immunogenicity (anti-emicizumab antibodies) on safety, efficacy, and/or clinical pharmacology and PK will be summarized adopting standard language/terminology.

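### The Arm C date split puts the pre-dose Week 25 labs, recorded vital signs and ECG outside the control period, leaving controls who switch on schedule with no routine post-baseline value

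*Protocol*

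**What the plan says.** Protocol 6.6 divides Arm C safety data by calendar date. Data up to the day before the switch go into the control-arm summaries, and "all safety data reported on or after the date of switching to active treatment will be reported separately". The synopsis appended to the SAP repeats the split: "all safety data reported up to the day prior to switching will be included in the" control-arm summaries. Neither text mentions measurements taken on the switch date before the first injection.

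The timing of that visit is fixed elsewhere in the protocol:

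- Section 4.3.2 speaks of "patients in Arm C who switch to emicizumab at Week 25".
- Appendix 1, footnote l, schedules an antibody sample for "Arm C immediately prior to the first injection at Week 25".
- The notes to Appendix 1 set the visit date: "Clinic visits should coincide with the day of emicizumab dosing".
- The same notes set the order within such a visit: "on those days the dose should be administered after blood draws and other assessments are conducted".

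SAP 4.7.3 to 4.7.5 plan lab shift tables, mean change from baseline for vital signs, and ECG change from baseline by arm and visit. SAP 4.7 gives no boundary rule for Arm C. SAP 4.1 describes the control period only as the time before the switch, with no time-of-day rule.

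**The concern.** The safety objective (Protocol 2.2) is a comparison with no prophylaxis, and its endpoints include laboratory abnormalities and changes in vital signs. For that comparison the control column needs at least one follow-up measurement. The Arm C schedule provides one routine occasion, at Week 25, taken after 24 weeks without prophylaxis and before any emicizumab. A split by date rather than by dose assigns it to the wrong period.

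Read literally, the three sets of change tables would then have no routine post-baseline control value for patients who switch as expected. The changes seen in Arms A and B could not be set against an untreated change at the same visit.

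**Working it through.** The plan gives no figure on this point to reproduce, so the check is a tally of Protocol Appendix 1 followed by the Section 6.6 rule. Screening or Week 1 is taken as baseline.

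**Arm C before the switch day**

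- Safety labs are marked at Screening and Week 1 only.
- The ECG is marked at Screening. A further one is conditional: "If screening ECG is abnormal, repeat at Week 1 (or Week 2 [or Week 5 for Arm C" applies to an abnormal screening trace.
- Vital signs are measured at Weeks 5, 9, 13, 17 and 21. Footnote f, attached to that row, limits eCRF entry of temperature, blood pressure, pulse and respiration to Weeks 1, 25 and 49, early termination or completion, and follow-up.

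**Arm C at Week 25**: labs, recorded vital signs and an ECG are all scheduled, before the dose and on the switch date.

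**Arms A and B, after Week 1 through Week 25**

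- Labs at Weeks 2, 3, 4, 5, 7, 9, 13, 17, 21 and 25, which makes 10.
- Recorded vital signs at Week 25, which makes 1.
- Unconditional ECGs at Weeks 5 and 25, which makes 2.

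Routine scheduled post-baseline records per patient:

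| Domain | Arm C control, as written | Arm C control, pre-dose Week 25 included | Arm A or B |
|---|---|---|---|
| Safety labs | 0 | 1 | 10 |
| Recorded vital signs | 0 | 1 | 1 |
| ECG | 0 | 1 | 2 |

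**Other readings of the schedule.** Protocol 3.1 says that "laboratory assessments will be collected as per the schedule of assessments and will be the same for all patients", apart from PK and anti-drug antibodies. If that sentence overrode the Arm C table, Arm C would have one ECG (Week 5) before the switch day. It would have 5 lab sets at its own visits (Weeks 5, 9, 13, 17, 21), or 9 if it also followed the visit calendar of Arms A and B. If footnote f did not apply to Arm C before the switch, there would be 5 recorded vital-sign sets.

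**What one Week 25 value would buy.** Planned sizes are 34, 34 and 17 (Protocol 6.1).

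- If 0 of 17 controls show an abnormality, the exact two-sided 95% upper limit is 1 − 0.025^(1/17) = 0.195, or 19.5%.
- For a difference in mean change, A or B against C, the 95% half-width is t(0.975; 49) × √(1/34 + 1/17) = 0.597, or about 0.60 SD.

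**The case against.** Several points on the other side have substance.

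- **The values are relabelled, not lost.** They are reported separately and would naturally serve as baseline for Arm C's emicizumab period, so an abnormality could still appear there. This stands: the loss is confined to the control column. That column, however, is the comparator in the safety objective.
- **The SAP body defines the periods by treatment state.** SAP 2 and 4.1 separate time on no prophylaxis from time after the switch, and a pre-dose value fits the former. A programmer might read it so. But the only explicit rule is the date rule, it appears in both documents, and it gives the opposite answer.
- **The vital-sign zero is less secure.** Footnote f explains non-entry by monitoring around injections, which does not describe Arm C before Week 25. It is nonetheless attached to the Arm C row and names Arm C in its text. The count of 0 holds only if it applies there.
- **Some control data remain.** Conditional ECGs, unscheduled tests, early terminations, and late or non-switchers can contribute. Switching is offered rather than compelled, so the number affected is at most 17 and not known exactly.
- **The effect is small.** Adverse events are collected throughout, and clinically significant lab or vital-sign abnormalities are reported as such (Protocol 5.3.5.5 and 5.3.5.6). This is correct, but such reports do not replace the planned change tables.
- **The remedy is partial.** One control lab set against ten still gives unequal chances of detecting an abnormality, so any worst-post-baseline summary would lean towards more findings on emicizumab. This is also correct, and it is why the comparison should be made at the same visit.

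**Conclusion.** The point holds. As written, Protocol 6.6 moves the only routine untreated follow-up labs, recorded vital signs and ECG out of the control summaries. For patients who switch at Week 25, the control column then has 0 routine post-baseline values in each of the three domains. The rule itself costs one record per patient per domain, for up to 17 patients; the rest of the lab difference (9 of the 10 sets) is how the schedule was drawn.

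The conclusion assumes that the Arm C table governs over the general sentence in Protocol 3.1, that footnote f applies to Arm C before the switch (needed for vital signs only), and that Screening or Week 1 is baseline. The documents do not define a safety baseline. If Screening alone were used, the Week 1 labs would formally count as post-baseline, but they are taken at enrolment and may be replaced by recent screening labs, so they give no follow-up.

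The consequence is limited to descriptive safety tables. Efficacy, type I error and adverse-event capture are untouched.

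**What to change.** - Add one sentence to Protocol 6.6 and one to SAP 4.7: Arm C assessments made on the switch date before the first emicizumab dose are the last control-period value and also the baseline for the Arm C emicizumab period. The scheduled Week 25 visit is treated as pre-dose, in line with the Appendix 1 notes.
- Within the lab, vital-sign and ECG summaries already planned, show change to Week 25 for Arms A and B beside Arm C control, so that the contrast uses the same visit.
- Reconcile the sentence in Protocol 3.1 with the Arm C schedule, and state whether footnote f applies to Arm C vital signs before the switch.

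The cost is the two sentences, two wording corrections and a change to the period flag in programming. The measurements are already scheduled, so no visits or samples are added.
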